11.0 STATISTICAL HYPOTHESIS AND METHODS OF ANALYSES

11.1 Power Calculation and Determination of Sample Size

In a previous controlled study assessing the change in EDS while in the CAE at Day 0, the observed mean (SD) treatment difference for the TrueTear device compared to the control was -13.4 (23.9). It is unknown what, if any, effect on the change in EDS while in the CAE will be with the TrueTear device application after 45 days of use. Using an estimated standard deviation of 25, 45 participants will provide over 90% power to detect a EDS reduction of 13 based on a one-sided test at an α of 0.025.

In the previous study, approximately 10% of the participants did not reach the application threshold during the CAE session. In order to allow for participants that discontinue the study before Day 45 or do not reach the application threshold in the CAE, approximately 60 qualified participants will be identified to initiate the study to ensure Day 45 results for 45 participants.

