11.4 Evaluability of Data

All participants who initiated at least one study application will be eligible for inclusion in the analyses. Participation in the study will be summarized by presenting the number of participants who were enrolled, the number of participants who completed the study, and the number of participants who did not complete the study due to not reaching the threshold or by reason of early discontinuation.

Full Analysis Set Population (FAS): The FAS population will include all participants who initiated at least one application of the TrueTear device at any point during the study.

Per protocol population (PP): The PP population is a subset of the FAS population, which did not have a major protocol deviation likely to seriously affect the primary outcome of the study. This population will be the secondary population for the effectiveness analyses and will also be used to summarize the primary and exploratory effectiveness variables. If the PP and FAS populations are exactly the same, then additional efficacy analyses on the PP population will not be performed.

Safety Population: The safety population will be the same as the FAS population.

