11.8 Effectiveness Analyses

The primary effectiveness variable will be the change in EDS between the time point preceding application and the subsequent time point following application. The primary effectiveness endpoint will be the analysis of the primary effectiveness variable for the FAS population at Day

45 without imputation. The analysis will use a paired *t*-test or Wilcoxon signed-rank test, as appropriate, and will be evaluated at a one-sided α of 0.025. If $\geq 5\%$ of the FAS population is missing the primary effectiveness variable at Day 45, a sensitivity analysis of EDS difference at Day 45 will be performed by imputing the missing EDS difference as zero. Study participants with a missing Day 45 result will be imputed one at a time and the analysis will be repeated. This process will continue until either the result is no longer statistically significant or all participants with missing results have been imputed. As an additional sensitivity analysis, missing values will be imputed using a random selection process from the available Day 45 results and the analysis will be repeated. This process will be performed 10 times and a single combined p-value for the 10 imputations will be obtained by a method described in Rubin³⁸ and in the SAS manual for PROC MIANALYZE.³⁹ If the study includes more than one site, summaries of the primary effectiveness endpoint without imputation will be presented by site.

The primary effectiveness analysis will be repeated in the PP population as a sensitivity analysis.

The exploratory effectiveness variables will be the difference in EDS at Day 0, the difference in dry eye discomfort using the [REDACTED] Calibra scale in the FAS population at Day 0 and Day 45 and the difference in Schirmer test results at Day 7. The analysis will be performed using the same method as the primary effectiveness variable. Statistical significance will be determined using a one-sided test at an α of 0.025.

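### Minor: with 10 random imputations and no stated seed, a borderline Day 45 result can give a combined sensitivity p-value on either side of 0.025.

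*Combined protocol and SAP*

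**What the plan says.** Section 11.8 analyses the primary endpoint in the FAS at Day "45 without imputation", by a paired t-test or a Wilcoxon signed-rank test; the test "will be evaluated at a one-sided α of 0.025". If at least 5% "of the FAS population is missing the primary effectiveness variable at Day 45", missing differences are set to zero one participant at a time. A further sensitivity analysis then fills the gaps by random draws from the observed Day 45 results: "This process will be performed 10 times and a single combined p-value for the 10 imputations will be obtained". The method cited is Rubin's, with the manual for PROC MIANALYZE. The section states no seed, does not say which degrees of freedom apply, and attaches no decision to the combined p-value.

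The 5% trigger may well be met. Section 11.4 says "The FAS population will include all participants who initiated at least one application of the TrueTear device at any point during the study", so a participant treated on Day 0 who has no Day 45 value stays in the FAS as missing. Section 11.1 plans that "approximately 60 qualified participants will be identified to initiate the study to ensure Day 45 results for 45 participants", and reports that in the earlier study "approximately 10% of the participants did not reach the application threshold during the CAE session".

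**The concern.** A sensitivity analysis for missing data is most useful when the primary result is only moderately significant. In that situation, 10 random draws leave visible noise in the combined test statistic. Without a fixed seed, re-running the same program on the same data can move the reported p-value across 0.025 in either direction. Section 11.1 says that the effect after 45 days is unknown, so a moderate result is possible. At stake is how robust the primary result appears in the report, not the primary result itself.

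**Working it through.** **Inputs.** One-sided alpha 0.025 and 10 imputations (11.8). Reduction 13, SD 25, 45 results from 60 starters (11.1). Assumptions: normal scores, the t-test branch (the Wilcoxon branch gives no estimate and standard error to combine directly), and missingness between 5% and 25%.

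**The plan's own figure.** Section 11.1 states: "Using an estimated standard deviation of 25, 45 participants will provide over 90% power to detect a EDS reduction of 13". The standard error is 25/√45 = 3.727, so the noncentrality is 13/3.727 = 3.49. Power is 92.7% by the noncentral t and 93.7% by the normal approximation. The statement reproduces.

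**Size of the noise, by hand (45 observed, 15 imputed).**
- Within-imputation variance: U = 625/60 = 10.417.
- Between-imputation variance of the mean: B = 15 × 625/60² = 2.604.
- Total with M = 10: T = U + (1 + 1/10)B = 13.281, so √T = 3.644.
- Seed-to-seed SD of the pooled mean: √(B/10) = 0.510, or 0.510/3.644 = 0.14 on the t scale.
- Primary p = 0.020 corresponds to a mean of 2.116 × 3.727 = 7.89. The pooled t is centred near 7.89/3.644 = 2.17, against a critical value of 1.972. The margin of about 0.19 is only about 1.4 seed SDs, before counting seed variation in T.
- At the planned effect the pooled t is near 13/3.644 = 3.57, more than 11 seed SDs clear.
- With M = 200, √(B/200) = 0.114, or about 0.03 on the t scale. The same borderline margin is then several seed SDs.

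**Simulation of the planned method** (one fixed data set per row, 45 + 15, M = 10, 20,000 seeds, Rubin's degrees of freedom):

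| Primary one-sided p | Combined p, 95% of seeds | Seeds significant at 0.025 |
|---|---|---|
| 0.0006 (planned effect) | at most 0.007 over all seeds | 100% |
| 0.010 | 0.002–0.018 | 99.6% |
| 0.020 | 0.006–0.034 | 87% |
| 0.025 | 0.008–0.042 | 73% |
| 0.030 | 0.010–0.050 | 55% |
| 0.040 | – | 25% |
| 0.050 | – | 8% |
| 0.10 | – | 0% |

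At primary p = 0.020, repeated runs put 12 to 13% of seeds above 0.025. With 200 imputations the range is about 0.011 to 0.018 and none exceed it. With less missing data and M = 10, about 7 to 8% exceed it at 6 of 60 missing, and 3% at 3 of 60.

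**Over new simulated trials** with 15 missing and M = 10, two seeds disagree in 2.5% of trials at the planned effect, in 1.0% of those with a significant primary result, and in about 7% of trials if the true reduction is 8. With 100 imputations the 2.5% falls to 0.7%.

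**Degrees of freedom.**
- The share of variance due to imputation is λ = 1.1 × 2.604/13.281 = 0.2157. Rubin's formula gives (M − 1)/λ² = 9/0.0465 = 193; the simulated median is about 225.
- Complete data on 60 participants carry 59. The small-sample version has an observed-data part of (60/62) × 59 × (1 − 0.2157) = 44.8, which combines to 1/(1/193 + 1/44.8) = 36.
- The critical value is 1.972 rather than 2.027, a one-sided error of about 0.028 rather than 0.025.
- At M = 200, λ = 1.005 × 2.604/13.034 = 0.201 and Rubin's formula gives 199/0.0403, about 4,900. Raising M without supplying EDF widens this gap.

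**The zero-imputation analysis on a similar case.** Primary p = 0.021 means a mean of 7.81. After 15 zeros the mean is 7.81 × 45/60 = 5.86. The SD is √[(44 × 625 + 45 × 7.81² − 60 × 5.86²)/59] = 21.9, giving t = 2.07 on 59 degrees of freedom and p = 0.0212. The zeros are identical, so neither a seed nor the order of imputation matters.

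**The case against.** The case against acting is substantial, and most of it stands.

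- **Nothing formal turns on this p-value.** A reader might infer that the seed could decide whether the trial succeeds. The documents do not support that: the primary test uses no imputation, and this is a supplementary analysis with no decision rule.
- **The affected cases are borderline.** Under the planned effect, the chance of a primary p between 0.010 and 0.025 is about 7%. At primary p = 0.010 only 0.4% of seeds exceed 0.025.
- **The 25% missing is an allowance, not a forecast.** It follows from 60 starters and 45 required results. The only observed rate cited is about 10% not reaching the threshold.
- **Ten imputations are not invalid.** Rubin's (1 + 1/M) term already allows for a finite number of draws. Relative efficiency at 25% missing is 1/(1 + 0.25/10) = 97.6%. But that figure describes the variance of the pooled estimate. It does not show that one reported p-value can be reproduced, which is the narrower point here.
- **More draws do not make this a better missing-data test.** With unlimited draws T tends to 10.417 + 2.604 = 13.02, below the 625/45 = 13.89 from the observed data alone. The combined p-value therefore settles below the primary one.
- **The small-sample degrees of freedom are not excluded.** The plan cites the procedure's manual without choosing an option, so this is a gap to close rather than an error.

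**Conclusion.** The point holds as a minor, nearly cost-free improvement in repeatability. With 10 draws and no seed in the public text, the combined p-value depends on the seed when the primary one-sided p lies roughly between 0.01 and 0.05 at 25% missing, and over a narrower range with less. At primary p = 0.020, about 12% of seeds exceed 0.025 with 15 of 60 missing and about 7 to 8% with 6 of 60. At the plan's own effect and SD, none of 20,000 seeds did.

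These figures rest on normal scores, SD 25, the t-test branch, the assumed missing fractions and Rubin's original degrees of freedom. The degrees-of-freedom point is secondary. It belongs here because it grows when the number of imputations is raised.

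**What to change.** In section 11.8:

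1. Replace 10 with at least 200 imputations.
2. Prespecify the random seed.
3. Run PROC MIANALYZE with the complete-data degrees of freedom, EDF = N − 1 (59 for 60 participants).
4. State that the result is read beside the zero-imputation analysis, because extra draws remove Monte Carlo noise but not the optimism of drawing directly from the observed values.

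The seed is needed as well as the larger number. More draws narrow the band of results that depend on the seed but do not eliminate it. For example, with 57 observed and 3 imputed values, primary p = 0.025 and small-sample degrees of freedom, 62% of seeds are still significant at 500 imputations and 38% are not.

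The cost is one number, one seed, one software option and one sentence, with seconds of computing. No participants are added and the primary analysis does not change.

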3.0 CLINICAL HYPOTHESES

After 45 days of TrueTear use, neurostimulation continues to result in a statistically significant reduction in eye dryness as exacerbated by exposure to the CAE.

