8.2 Participant Training, Device Dispensing, and Home Use

On Day 0, participants will be provided with a TrueTear and disposable tips to take home with them and use daily per the Instructions for Use (IFU). Participants will receive training to perform intranasal neurostimulation and will receive a user guide. Following device training and prior to entering the CAE, devices for home use will be dispensed to participants. The serial number of the unit and the lot number of disposable tips will be documented in the participant's CRF.

Participants will undergo stimulation for the first time on Day 0 during the CAE session where they will be instructed to apply stimulation for approximately three minutes. Training will include instruction on the following points:

- Between study visits, participants will be asked to perform neurostimulation at least two times per day up to as many as 10 times per day, as needed. Each stimulation should last no longer than three minutes. Participants should be instructed that the device has a single-day stimulation limit of 30 minutes at which point the device will time-out.
- Participants will be asked to fully charge the device before first use and to re-charge daily.
- After using the device, participants will be instructed to clean the system with tissue or an alcohol pad if necessary prior to placing the cover to protect the tip between uses.
- Participants should be instructed to replace the disposable tip daily according to the IFU and that the used tip should be discarded in trash.

For the device application, participants will be instructed to place the tips of the TrueTear into both nostrils simultaneously towards the top and front of the nose (as in [Figure 2](#)). They will be told to turn on the unit by holding down the + button for approximately two seconds. There are five stimulation intensity levels and participants may adjust the level by pressing the + or – buttons to obtain a gentle tingling sensation. Participants will be told they can cease stimulation by holding down the – button for approximately two seconds on the base unit or by withdrawing the tips from the nostrils. Participants will be instructed to replace the Tip if they do not feel any sensation.

Figure 2 Use of the TrueTear

(L) Starting position and (R) Correct application position by inserting the disposable tips fully into the nasal cavity and to the front of the nose.

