11.2 Statistical Hypotheses and Level of Significance

The null hypothesis is, after 45 days of TrueTear use, neurostimulation fails to result in a statistically significant reduction in EDS exacerbated by exposure to the CAE.

The alternative hypothesis is, after 45 days of TrueTear use, neurostimulation will result in a statistically significant reduction in EDS exacerbated by exposure to the CAE.

The hypothesis can be expressed as:

$$H_0: \Delta \leq 0 \text{ mm}$$

$$H_A: \Delta > 0 \text{ mm}$$

where Δ represents the change in EDS score, symptom relief, from the TrueTear application. Statistical tests for the primary and exploratory effectiveness variables will be one-sided and evaluated at an α of 0.025.

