15.2.5.2 Eye Dryness Score (EDS) Visual Analog Scale (VAS)

Participants will be asked the following question regarding eye dryness as specified in the protocol. On the CAE visit days, EDS will be collected upon entering the CAE and every 5 minutes during CAE exposure. The participants will be asked to rate their current eye dryness (both eyes simultaneously) by placing a vertical mark on the horizontal line to indicate the level of eye dryness; 0 corresponds to “no discomfort” and 100 corresponds to “maximal discomfort.” The assessment line length of the scale will be 100 mm and will be similar to the following depiction:

Please rate your current eye dryness by drawing a vertical line on the line below:

15.2.5.1 [REDACTED] Calibra™ Ocular Discomfort Scale

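### Should section 11.8 prespecify a paired Day 45 minus Day 0 estimate of EDS relief?

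*Combined protocol and SAP*

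**What the plan says.** Section 2.0 sets the objective as characterizing acute symptom relief in the CAE after 45 days of use. Section 3.0 expects that, by then, "neurostimulation continues to result in a statistically significant reduction in eye dryness as exacerbated by exposure to the CAE". Section 11.2 tests Δ ≤ 0 against Δ > 0, where Δ "represents the change in EDS score, symptom relief, from the TrueTear application". Sections 6.1.1 and 11.8 carry this out as a one-sided test at 0.025 of the Day 45 change against zero, in the FAS and without imputation.

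For the earlier visit, section 11.8 says: "The exploratory effectiveness variables will be the difference in EDS at Day 0". The list goes on to the discomfort scale at Day 0 and Day 45 and the Schirmer test at Day 7, all analysed by the primary method. The pairing in that method is before against after application within one session. It is not one visit against another.

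The data for a between-visit contrast will exist. Section 15.2.5.2 states: "On the CAE visit days, EDS will be collected upon entering the CAE and every 5 minutes during CAE exposure". The FAS in section 11.4 takes in "all participants who initiated at least one application of the TrueTear device at any point during the study".

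**The concern.** The hypothesis uses the word continues, and section 11.1 concedes of the Day 45 effect: "It is unknown what, if any, effect on the change in EDS while in the CAE will be". With a CAE session at each end of the 45 days, a reader will set the two mean changes side by side and ask whether the response has faded. The plan does not equip that reader, for two reasons.

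- Separate means and SDs do not reveal the correlation between visits, so no paired interval can be built from them.
- The two means may rest on different people. Section 11.1 expects discontinuations and reports that in the previous study "approximately 10% of the participants did not reach the application threshold during the CAE session".

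What would be at stake is any statement about persistence or waning. It would rest either on a comparison of partly different groups or on a contrast whose participants and method were chosen after the results were known.

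**Working it through.** **Inputs.** From section 11.1: SD 25, reduction 13, n = 45, one-sided α 0.025, about 60 starting, about 10% not reaching the threshold in the previous study. Assumed, because the documents do not give them: the same SD of 25 at both visits, the correlation ρ between the two visits' changes, and how far early leavers differ from the rest. The SD of 25 follows a device-versus-control figure (SD 23.9), so applying it to a within-person change is itself an assumption.

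**1. The plan's own figure.** Noncentrality = 13 / (25/√45) = 13/3.727 = 3.49. With 44 degrees of freedom the power is 92.7% (normal approximation 93.7%). The stated figure of over 90% is reproduced.

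**2. What a significant primary result shows.** The smallest significant mean relief is t(0.975, 44) × 25/√45 = 2.0154 × 3.727 = 7.5 mm. Success shows relief above zero. It does not show that 13 mm was kept, and the hypotheses do not ask for that.

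**3. Precision of a paired contrast.** SD of the difference = 25 × √(2(1−ρ)). Half-width = t × SD/√n, with t = 2.0154 for 45 pairs and 2.0227 for 40 (about 10% of the 45 lacking a Day 0 value).

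| ρ | SD of difference | 45 pairs | 40 pairs |
|---|---|---|---|
| 0 | 35.4 | 10.6 mm | 11.3 mm |
| 0.3 | 29.6 | 8.9 mm | 9.5 mm |
| 0.5 | 25.0 | 7.5 mm | 8.0 mm |
| 0.7 | 19.4 | 5.8 mm | 6.2 mm |

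**4. Comparison with an unpaired reading.** If 60 × 0.90 = 54 contribute at Day 0 and 45 at Day 45, treating them as independent gives 1.985 × 25 × √(1/45 + 1/54) = 10.0 mm.

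- For ρ from 0.3 to 0.7, pairing narrows this by 11% to 42% with 45 pairs, or 6% to 38% with 40.
- At ρ = 0 pairing is wider.
- Break-even is 1 − (10.02/10.62)² = 0.11 with 45 pairs and 1 − (10.02/11.31)² = 0.22 with 40.

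The plan does not propose the unpaired comparison. It is only a yardstick.

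**5. Different contributors.** 54 − 45 = 9, and 9/54 = 17% would count only at Day 0. If they differ from the other 45 by d, the Day 0 mean moves by d × 9/54: 1.1 mm for d = 6.5 and 2.2 mm for d = 13. Both values of d are assumed. The shift is smaller than every half-width above. The 60 and 45 are approximate, and 60 is a cushion, so fewer may be lost.

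**6. Ability to detect waning.** With 45 pairs, the power to detect loss of half the planned effect (6.5 mm) at one-sided 0.025 is 23%, 30%, 40% and 60% for ρ = 0, 0.3, 0.5 and 0.7.

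**The case for a change.** The best case for adding the contrast is that it costs one table from data already collected, that the protocol itself raises the matter of continued effect, and that a significant Day 45 result at 7.5 mm is compatible with substantial waning from Day 0. Naming the participants and the method in advance would also remove any choice made after seeing the results.

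Part of this stands. The contrast is absent from the readable text of section 11.8, and the separate summaries cannot give a paired interval. Exploratory text in the synopsis and section 6 is blacked out, so its absence from the whole plan cannot be confirmed.

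The rest is weaker.

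- The remark in section 11.1 is a sample-size caveat about the effect at Day 45. The size of that effect is described by the mean, SD, median and range that section 11.5 plans for continuous variables, with no need of Day 0.
- The room for choice afterwards is small, since participants with both values are the obvious set.
- Section 11.4 lists not reaching the threshold among the reasons for not completing the study. It does not name the visit. If Day 0 is meant, those with a Day 45 value are a subset of those with a Day 0 value, and the 40-pair case falls away.
- The contrast would not isolate a device effect. Section 8.2 says: "Participants will undergo stimulation for the first time on Day 0 during the CAE session". Novelty may fade after that, and section 8.1.3 allows other eye products between visits. The estimate would also be limited to those who completed both sessions.

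**Conclusion.** No change to the plan is needed. Followed as written, section 11.8 gives a valid test of the one question that sections 2.0, 3.0 and 11.2 pose, namely whether relief is present at Day 45. The paired contrast answers a further question that the protocol does not set. It would alter no planned result or decision, and the sample size and α would stay as they are.

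Its value as an extra is modest and not assured. With 45 pairs the half-width is 10.6 mm at correlation 0 and 5.8 mm at 0.7, so a gain over the 10.0 mm yardstick needs a correlation above about 0.11 (0.22 with 40 pairs). The possible distortion from differing contributors is 1.1 to 2.2 mm, on assumed differences. All these figures rest on SD 25 at both visits and on correlations that the documents do not give.

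The primary result should be read as a reduction different from zero at Day 45, and not as proof that the Day 0 response was maintained. An analyst asked about persistence would naturally take participants with both values, report their number, both visit means and the paired difference with a two-sided 95% interval, and label it descriptive.
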